2.2.2.4 Secondary illness

Note that although the secondary illnesses of interest defined in the protocol do not include the term LRTC this term will be included to ensure other LRTCs not captured as pneumonia or bronchitis will be reported.

- Incidence of any secondary illnesses such as LRTC (otitis media, bronchitis, pneumonia or sinusitis) for all patients at any time during the study.
- Incidence of secondary illnesses, i.e. LRTC, for all patients at any time during the study that are treated with antibiotics. Antibiotic use for secondary illnesses will be selected from the concomitant logs prior to database lock. This selection will be based on a medical decision. Cases will be identified as any antibiotic treatment received for the above secondary illnesses.
- Time to initiation of treatment with antibiotics from randomisation.

Note: Although this endpoint was defined in the protocol using randomization date and time as the start of the time period, the time from treatment initiation will be used to define the start of the time period. This decision has been made in order to remain consistent with other time to endpoints in this study. The time between randomization and treatment initiation will be checked to ensure time differences across the two treatment groups are balanced.

2.2.2.5 Hospitalisation

- Incidence of hospitalisations for all patients. Given that patients will be in the study for a short period, i.e. ~40 days, we envisage a maximum of 1 hospitalisation per patient. Thus, probabilities of hospitalisation will be compared across treatment arms.
- Duration of hospitalisation (in days), for those who are hospitalized, as recorded directly on the Case Report Form (CRF) for all patients. Given that there may be few hospitalisations, this subgroup analysis will only report median times and ranges by treatment arm.

2.2.3 Exploratory Efficacy Outcome Measures

Not applicable.

2.2.4 Pharmacokinetic Outcome Measures

If estimable, the following model-predicted PK parameters for oseltamivir and oseltamivir carboxylate will be calculated on the basis of the oseltamivir established population PK model.

- Steady-state area under the concentration-time curve from 0 to 12 hours (AUC_{0-12}).
- Maximum plasma concentration C_{max} .

- Trough plasma concentration C_{trough} .

If appropriate, the following model-predicted parameters may also be included.

- Elimination half-life ($t_{1/2}$).
- Time to maximum concentration (t_{max}).
- Elimination constant (k_e).
- Apparent Clearance (CL/F).
- Apparent volume of distribution (V_c/F).
- Apparent total clearance of metabolite (CL_m).
- Last measurable concentration (C_{last}).
- Time to last measurable concentration (t_{last}).

2.2.5 Safety Outcome Measures

The endpoints used to support the co-primary objective of safety are the following:

- Incidence and severity of AEs (including influenza-associated complications and abnormal findings from physical examinations), SAEs, and reasons for the discontinuation of any study medication. All SAEs and AEs will be tabulated including their clinical severity.
- Change from baseline in vital signs (weight, temperature, respiratory rate, blood pressure and pulse rate).
- Change from baseline in laboratory parameters (AST, ALT, total bilirubin, urea, creatinine, CBC and differential blood cell count, i.e. neutrophils, lymphocytes, monocytes, eosinophils, basophils).
- Lab abnormalities by baseline and visit status (see SOP COG 3007 for expected normal ranges).
- Incidence of tissue rejection or GVHD (Graft Versus Host Disease) in transplant patients.

Note: Incidence of transplant rejection or GVHD in transplant patients has been defined in the protocol as both a primary and secondary endpoint. It will be reported as a primary safety endpoint.

2.2.6 Resistance Outcome Measures

The following endpoint is used to support the co-primary objective of resistance.

Resistance is defined as the presence of oseltamivir resistance in samples identified by sequencing of the neuraminidase (NA) and haemagglutinin (HA) genes (**genotypic resistance**) or by oseltamivir IC_{50} determination by a NA inhibition assay, using statistical outlier rules (**phenotypic resistance**). Resistance (genotypic, phenotypic and pooled) will be summarized per age (adults, paediatrics), dose group, viral type and subtype.

For patients who are infected with both A and B virus types or two Flu A viruses the following algorithm will be applied:

- "A" if RT-PCR A is positive (i.e. not NEGATIVE) and RT-PCR B is NEGATIVE at the 1st timepoint with RT-PCR results.
- "B" if RT-PCR B is positive (i.e. not NEGATIVE) and RT-PCR A is NEGATIVE at the 1st timepoint with RT-PCR results.
- "AB" if RT-PCR A and RT-PCR B are positive (i.e. not NEGATIVE) and Mixed Flu A if both RT-PCRs for Flu A subtyping are positive (i.e. not NEGATIVE) at the 1st time point with RT-PCR results.
- "UNK" otherwise.

For patients with a mixed infection, samples from time points with only one detected Flu type will be included in the overall virology analyses. Entire virology data will be described separately per patient.

2.2.6.1 Genotypic resistance

Baseline and post-baseline genotypic resistance is defined as the presence of oseltamivir resistance mutations in the NA or HA genes identified by sequencing of influenza viruses isolated from nasopharyngeal samples.

Genotypic resistance calculation: Presence of genotypic resistance (yes/no), together with the specific resistance mutations will be identified (see USPI list in [Appendix 6](#)) for each nasopharyngeal sample and will be listed.

Note: a H274Y-specific RT-PCR assay was performed for some H1N1 samples of season 2008-2009 to determine baseline genotypic resistance and results will be also included.

2.2.6.2 Phenotypic Resistance

Baseline and post-baseline phenotypic resistance is defined as the presence of phenotypic resistance identified by oseltamivir IC₅₀ determination, using statistical outlier rules and in accordance with the algorithm described in surveillance studies ([Sheu TG et al 2008](#), [Okomo-Adhiambo M et al, 2010](#)).

Phenotypic resistance calculation: The mean IC₅₀ of the baseline (pre dose Day 1 result) samples of all patients will be calculated separately for each virus subtype. Extreme outliers will be defined as any baseline or post-baseline IC₅₀ values > 10-fold the baseline mean IC₅₀. The baseline IC₅₀ distribution statistics (i.e. mean, standard deviation [SD], median, 75th percentile [X_{0.75}]) will then be re-calculated excluding any baseline extreme outliers previously identified. Outliers will be defined as any baseline or post-baseline IC₅₀ values less than 10-fold the baseline mean, but more than three interquartile ranges (IQRs) greater than the

baseline third quartile ($X_{0.75}$) ($> [X_{0.75} + \{3 \times IQR\}]$). Outliers and extreme outliers will be considered to have phenotypic resistance.

Note: the phenotypic resistance algorithm assumes that the IC_{50} samples are normally distributed. Appropriate transformations will be considered if this assumption is not met. Furthermore, alternative algorithms (e.g., fold-changes, pooling of NA subtypes) may be used if the number of IC_{50} samples per NA subtype is considered small.

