4.1.3 Modified Intent To Treat infected (mITT_i) Population

All patients randomized to a particular treatment, regardless of whether they received that treatment or not, and received at least one dose of study drug and with central laboratory confirmation of influenza infection, excluding patients infected with oseltamivir-resistant influenza at baseline, will be included in the mITT_i population. This population will also be used to summarize all efficacy and resistance endpoints because it will render least biased effect estimates. This population was not defined in the protocol.

The definition of oseltamivir-resistant influenza at baseline is defined in Section 2.2.6. Decisions on patient exclusion from the ITT, ITT_i and mITT_i population sets will be made by the statistician and study scientist after database closure. Excluded patients will be documented along with the reason for exclusion.

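### The screen for extreme IC50 values uses a mean that contains those values, so once about 10% of a subtype's baseline samples are resistant it cannot remove them all and the limit for emergent phenotypic resistance rises

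*SAP*

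**What the plan says.** Section 2.2.6.2 defines phenotypic resistance in two steps. First, the mean IC50 of the "baseline (pre dose Day 1 result) samples of all patients will be calculated separately for each virus subtype". The text continues "Extreme outliers will be defined as any baseline or post-baseline" IC50 above 10 times that mean. Second, the baseline mean, SD, median and quartiles are computed again, "excluding any baseline extreme outliers previously identified". A baseline or post-baseline value below 10 times the mean, but "more than three interquartile ranges (IQRs) greater than the" third quartile of the retained baseline values, is then an outlier. "Outliers and extreme outliers will be considered to have phenotypic resistance".

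A note in the same section says that the rule presumes normally distributed IC50 values. Transformation is to be considered if that fails, and other algorithms are allowed if a subtype has few samples. No test, threshold, transformation or alternative is fixed.

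Section 2.2.6.1 describes sequencing, and adds that "a H274Y-specific RT-PCR assay was performed for some H1N1 samples of season 2008-2009 to determine baseline genotypic resistance". Sections 4.1.2 and 4.1.3 define ITTi and mITTi "excluding patients infected with oseltamivir-resistant influenza at baseline". Section 4.7 reports the proportion of patients with post-baseline genotypic or phenotypic resistance, with a Clopper-Pearson 95% interval, as a co-primary result.

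**The concern.** The first step exists to clear resistant values out of the reference distribution before its quartiles are used. But each value is compared with a mean that it helps to form, so a group of resistant samples raises the bar it has to clear. Section 2.2.6.2 takes the samples of all patients. Patients who are resistant at baseline leave the analysis populations, but their IC50 values stay in the reference set unless the screen removes them.

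What is at stake is the phenotypic half of the co-primary resistance endpoint, the only route by which resistance without a listed substitution is counted. A raised limit can only lower that count. With 75 evaluable patients per arm (section 2.3), each missed patient moves the rate by 1/75 = 1.3 percentage points, and Table 1 plans for observed rates of 0 to 10.7%. The same limit also defines baseline phenotypic resistance, hence who is excluded from ITTi and mITTi, and the outlier and sensitive groups whose mutations section 4.7 compares.

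**Working it through.** **Inputs from the SAP.** The limit of 10 times the arithmetic mean, the single recalculation, and the limit of third quartile plus 3 IQR (section 2.2.6.2); 75 evaluable patients per arm (section 2.3). The SAP states no operating figure for the IC50 rule, so there is none to reproduce. The Table 1 intervals do reproduce exactly with 0, 1, 2, 4 and 8 events in 75.

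**Assumptions, not in the SAP.** The share f of a subtype's baseline samples that are resistant (0 to 30%), the fold R of resistant over sensitive virus, and the spread of IC50.

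**Step 1, a bound that needs no assumption.** Let m of n positive values exceed 10 times their mean. Their sum alone exceeds 10 × m × mean, and the total is n × mean. So 10m < n, or m < n/10. With n = 40 at most 3 values can be removed; with n = 10 or fewer, none.

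**Step 2, resistant samples sharing one fold R (sensitive IC50 = 1).** Removal needs R > 10[(1 − f) + fR], that is R > 10(1 − f)/(1 − 10f).

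| f | Fold needed for removal |
|---|---|
| 2% | 9.8/0.80 = 12.2 |
| 5% | 9.5/0.50 = 19 |
| 8% | 9.2/0.20 = 46 |
| 9% | 9.1/0.10 = 91 |
| 10% or more | none suffices |

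For example, with R = 300: at f = 5% the bar is 10 × (0.95 + 15) = 159.5, so the group is removed. At f = 10% it is 10 × (0.90 + 30) = 309, so it is not.

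**Step 3, the full two-step rule by simulation.** Log-normal IC50, ln SD 0.5 in both groups, R = 300, n = 40. The third column is the share called sensitive among post-baseline samples centred on an assumed 6-fold rise.

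| f | Outlier limit (fold over sensitive) | 6-fold rises missed |
|---|---|---|
| 0 | 3.4 | 13% |
| 10% | 3.8 | 19% |
| 15% | 4.5 | 29% |
| 20% | 5.7 | 46% |
| 25% | about 145 | 96% |
| 30% | about 720 | 100% |

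At 5% about 93% of resistant baseline samples are removed and the limit hardly moves. At 10% about 42% are removed; at 20%, 0.28 of 8. Even so, up to 20% all 300-fold samples are still flagged, because they lie above the quartile limit. From about 25% the third quartile falls among the resistant values; at 30%, 94% of 300-fold post-baseline samples are called sensitive.

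**Step 4, alternatives under the same settings.** Screening at 10 times the median removes essentially all 300-fold baseline samples and holds the limit at about 3.3-fold through 30%. Running the whole rule on the log scale also removes them, but its limit is near 9-fold and it misses about 74% of 6-fold rises at every level of contamination.

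**The case against.** The strongest reply is the note in section 2.2.6.2. A reference set in which 10 to 30% of values are 300-fold higher is plainly not normal, so the note would prompt a transformation, and on the log scale the screen clears 300-fold contamination completely. Small subtypes have their own escape clause. Both are true, but neither is fixed in advance. The log version also buys its robustness with a much higher limit, and it is robust only to high-fold contamination. With baseline virus only 10-fold above sensitive, its limit moves from about 10-fold with none resistant to about 29-fold at 20%.

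Further objections stand and limit the point:

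- A reader might infer that the screen never removes resistant values. It works well at 5%. With unequal folds at 10% or more it can still remove the highest; what it cannot do is remove all of them.
- A reader might infer that the reference set is known to be contaminated. The SAP gives no baseline resistance rate. The H274Y assay shows that baseline resistance was looked for in some samples. It does not show how often it was found, or that those samples have IC50 values in the set.
- A reader might infer that the co-primary rate as a whole is biased. Genotypic or phenotypic resistance counts, so a sample with a listed mutation is counted whatever the limit.

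**Conclusion.** The point holds as a conditional weakness in the rule. The 10% bound is exact and follows from section 2.2.6.2 alone. Its consequence depends on how common baseline resistance is within a subtype, which the SAP does not say:

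- **At 5%:** negligible.
- **From 10% to about 20%:** the limit rises from 3.4-fold to between 3.8- and 5.7-fold, and the loss is confined to low-fold emergent resistance without a listed mutation.
- **From about 25%:** the phenotypic rule fails outright.

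These sizes rest on the assumed sample number, spread and folds. The document does not support saying that the co-primary result is wrong. It does support changing a step that stops working where it is most needed, since the notes meant to protect it commit to nothing.

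**What to change.** In section 2.2.6.2, define extreme outliers as values more than 10 times the baseline median for the subtype, not the mean. Make the same replacement in the upper bound of the outlier definition, then recalculate the quartiles as planned. State this before treatment allocation is released (section 2.4).

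Add one sensitivity analysis that rebuilds the reference set without baseline samples carrying an Appendix 6 substitution or H274Y by RT-PCR. Keep that filter out of the main rule. Otherwise phenotype would depend partly on genotype, and the section 4.7 comparison of mutations in outlier and sensitive samples would become circular.

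The cost is a small wording change, one extra run on data already collected, and a small departure from the cited surveillance algorithm, to be stated as such. The median screen is not a complete cure: baseline virus only about 10-fold above sensitive sits at the limit and will be removed only in part.

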2.3 DETERMINATION OF SAMPLE SIZE

The sample size has been chosen to provide an adequate number of patients to estimate the development of resistance (genotypic and/or phenotypic) with reasonable precision. Assuming that 90% of enrolled patients will have laboratory-confirmed influenza, there will be 75 patients in each treatment arm in the population evaluable for the development of resistance. The following table shows the 95% Pearson-Clopper confidence intervals that would result with a sample size of 75 patients in a treatment arm if certain event rates are observed in the study.

Table 1 Expected confidence intervals associated to specific event rates

Observed Rate (%)	95% Confidence Interval
0.0	0.0-4.8
1.3	0.0-7.2
2.7	0.3-9.3
5.3	1.5-13.1
10.7	4.7-19.9

A total of 83 patients will be enrolled per arm and will be evaluable for the assessment of safety. This number of patients would provide estimates of adverse event rates with similar precision (see [Table 1](#)).

The sample size of 75 patients per group will have 66% power to detect a clinically relevant difference (CRD) between active treatment and historical placebo of 34 hours in time to resolution of symptoms, assuming a common standard deviation (SD) of 98 hours, using a 2-sided 10% alpha. The CRD and SD reflect those used to power the original study (original protocol). This has been calculated in EAST version 6.0, based on a Wilcoxon sign rank test. As no formal hypothesis will be tested in this study, the use of a 2-sided 10% alpha will be reflected by the use of 90% CIs.

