4.4.2.2 Comparison of TTR of All Symptoms to Historical Control

It is unethical to treat IC patients with placebo. Nevertheless, it is important to ascertain whether treating IC patients for influenza is still better than not treating them. Given the ethical constraint, the next best possible comparison available is against historical placebo controls. Thus, any difference between these two groups will be due to both IC status (yes/no) and oseltamivir effect. It will not be possible to differentiate both effects statistically. Historical controls will come first and foremost from pivotal historical oseltamivir studies where otherwise healthy (OwH) were enrolled. The main comparison of active treatment with historical control placebo will be based on a 1:1 matching of all adult NV20234 patients with OwH placebo patients from the pivotal studies. All patients in the adult mITTi population will be matched to historical patients (from the pivotal studies) that received a placebo.

There are three types of matches in order of priority:

1. Patients will be matched 1:1 within viral strain and then by age with ± 5 years caliper (the lowest limit being 18) and gender. Any remaining unmatched individual will be matched by age and gender alone. Only

pivotal studies will be used. Outputs in [appendix 5](#) refer to this matching rule.

2. Patients will be strictly matched 1:1 by age as above, gender and influenza strain. Only pivotal studies will be used. There will probably leave more unmatched patients but those matched will be more similar than in 1.
3. Patients will be matched 1:>1 as in 1 above using pivotal and non-pivotal but relevant historical studies. Additional matching by time between symptoms onset and first treatment (possibly with a caliper) will be used if closer matching is required. This is a sensitivity analysis captured in section [4.4.4](#).

In cases where those matching rules are not sufficient, i.e. more than one patient in the 1:1 placebo matching, an additional rule will be the elapsed time from first symptoms to first dose. If several matches are still available in the 1:1 ratio, one match will be chosen at random (the seed of the random number generator will be kept for reproducibility).

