Any patient from study NV20234 who has not been matched will not be included in these analyses. Matches will be done independently for historical placebo and historical treated. Modifications of the matching rules above may be permitted if scientifically required, e.g. matching by time in 3 above requires a window. The ITTi population in historical studies is equivalent to the current mITTi population.

The pivotal studies to be used are: WV15671 (18-65y, OwH, USA, placebo-conventional-double) and WV15670 (18-65y, OwH, Europe, Canada, Hong-Kong, placebo-conventional-double). Potential additional studies include: WV15730 (18-65y, OwH), M76001 (13-80y, OwH, placebo-conventional) and WV15758 (1-12y, OwH, placebo-conventional).

A similar comparison may be done between current IC patients and historical patients defined as at risk. There may be a 1:1 and 1:>1 matching ratios. The historical studies with patients at risk include WV15812 (≥ 13 y, placebo-conventional) and WV15872 (≥ 12 y, placebo-conventional). Additional studies in elderly (>65 years of age) are: WV15819, WV15876, WV15978 and WV15707 (see [Appendix 4](#)).

The following median differences in TTR of all symptoms (90% and 95% CIs) will be reported:

1. Comparison of conventional dose with matched placebo.
2. Comparison of double dose with matched placebo.
3. Comparison of combined conventional and double dose with combined matched historical placebo (if the results of the NV20234 dose group comparisons suggest responses are similar).

To aid interpretation of the results, the median TTR of all symptoms and associated 90% CIs will be plotted against historical placebo responses for a) NV20234 conventional dose b) NV20234 double dose c) NV20234 combined dose groups.

In addition to the comparison of NV20234 active with placebo patients from the pivotal studies, a *treatment* historical control dataset will be created from the same adult treatment studies, matching NV20234 patients randomized to the conventional dosing arm with the conventional dose from the adult treatment studies. This will enable an informal comparison of the treatment response of IC patients with the treatment response in otherwise healthy patients. Patients will be matched using the same rules as those for historical control.

The full specifications for historical control groups can be found in [Appendix 4](#). The final set of historical placebo patients will be confirmed prior to treatment unblinding and database lock.

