6. APPENDIX 1: PROTOCOL SYNOPSIS

TITLE: A DOUBLE BLIND, RANDOMIZED, STRATIFIED, MULTI-CENTER TRIAL EVALUATING CONVENTIONAL AND DOUBLE DOSE OSELTAMIVIR IN THE TREATMENT OF IMMUNOCOMPROMISED PATIENTS WITH INFLUENZA

PROTOCOL NUMBER: NV20234

VERSION NUMBER: F

EUDRACT NUMBER: 2006-002468-24

IND NUMBER: 53,093

TEST PRODUCT: oseltamivir (Tamiflu® RO 64-0796)

PHASE: IIIb

INDICATION: Treatment of influenza in immunocompromised patients

SPONSOR: F. Hoffmann-La Roche Ltd

Objectives

Primary

To evaluate prospectively the safety and tolerability of oseltamivir for the treatment of influenza in IC patients under standard and double dose, and characterize the effects of oseltamivir in IC patients on the development of resistant influenza virus (see 4.6).

Secondary

To evaluate the effects of conventional and double dose oseltamivir in IC patients on:

- The population pharmacokinetics of *both oseltamivir and oseltamivir carboxylate* in IC patients with confirmed influenza infection, through the application of established population pharmacokinetic (PK) models to the sparse plasma concentration data generated.
- The virologic course of influenza (proportion shedding and viral loads at different timepoints)
- The time to resolution of influenza symptoms
- The clinical course of influenza (fever, symptoms, secondary illnesses as evidenced by otitis media, bronchitis, pneumonia, or sinusitis)
- To explore the relationship of metrics of exposure (e.g., AUC, C_{min}) to relevant pharmacodynamic endpoints

Study Design

Description of Study

This is a double-blind, randomized, multi-center trial of twice daily, conventional and double dose oseltamivir for the treatment of influenza in IC patients. Patients will be stratified by age (<13 vs. >12 years), transplant status (yes vs. no), time since onset of flu symptoms and treatment start (up to 96 hours) (≤ 48 vs. >48 hours) and vaccination status (yes vs. no).

Number of Patients

A minimum of 166 (83 per arm) to allow an adequate number of influenza A patients per arm; including 50 transplant recipients *and at least 15 paediatric patients*.

Number of Centers

Approximately 125 centers in the Northern and Southern Hemispheres

Target Population

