Patients immunocompromised due to a primary or secondary immunodeficiency, 1 year of age and older (*the paediatric and adolescent patients will be defined as 1 year to less than 18 years of age*). The patients will be positive for influenza by a rapid diagnostic test, PCR or viral culture at baseline.

Length of Study

The study comprises 10 days of treatment with follow up visits approximately 5 and 30 days later as shown in the schedule of assessments. Study medication will be administered twice daily over 10 days for a total of 20 doses. A rapid diagnostic test for influenza will be performed at the end of the 10 days of treatment. Patients still having influenza based on the rapid diagnostic test will be treated per the local standard of care by the principal investigator, and any medication provided during the follow-up period should be captured in the CRF.

Procedures (summary)

The key procedures are:

- Blood draws for serum chemistry, hematology, serology, and PK assessments (for those patients who provide additional consent to participate in the PK assessments).
- Nasal and throat swabs for viral culture and RT-PCR.

Assessments of:

Safety

The safety laboratory assessments in this study, including the assessment of serum chemistry and hematology will be carried out at a central laboratory. Serum chemistry assessments comprise AST, ALT, total bilirubin, urea and creatinine. Hematology assessments include CBC and differential count. The total volume of blood loss for laboratory assessments will be approximately 20 mL for the entire duration of the study.

Protection of patient confidentiality (Section 16) will extend to any data generated from the assaying of these samples. Biological samples taken from all patients may be infectious and will be classified as “diagnostic specimens” for dispatch purposes.

When clinically indicated, the investigator may draw blood for serum creatinine to be assessed at the local laboratory during the study to calculate creatinine clearance

Resistance

Development of resistance

Efficacy

The efficacy laboratory assessments are used for laboratory confirmation of influenza. These are:

Nasal and throat swabs. Two nasal and one throat swab will be collected as described in the Schedule of Assessments. All swabs are sent to a central laboratory for RT-PCR and viral cultures. Influenza virus shedding will be assessed.

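### The 66% power against historical placebo rests on 75 patients of all ages per arm; the comparison uses adults only, about 68 per arm at an enrolment of 166, which gives about 62–63%

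*SAP*

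**What the plan says.** Section 2.3 assumes that 90% of enrolled patients will have laboratory-confirmed influenza and concludes that "there will be 75 patients in each treatment arm in the population evaluable for the development of resistance". With 83 enrolled per arm, that is the 90% share rounded up, and no age restriction is applied. The same section then uses the 75 for efficacy: "The sample size of 75 patients per group will have 66% power to detect a clinically relevant difference (CRD"). The difference is 34 hours against historical placebo, with a common SD of 98 hours and a two-sided 10% alpha. The test is named as a Wilcoxon signed-rank test.

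Section 4.4.2.2 describes the main historical comparison as "a 1:1 matching of all adult NV20234 patients with OwH placebo patients from the pivotal studies". It draws on the adult mITTi population and adds: "Any patient from study NV20234 who has not been matched will not be included in these analyses". Table A4.1 in Appendix 4 matches adult mITTi patients, and Appendix 5 lists the age group for this output as adults. Section 4.4 defines adults as 18 years or older.

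Appendix 1 gives the enrolment as "A minimum of 166 (83 per arm) to allow an adequate number of influenza A patients per arm", a total that includes "at least 15 paediatric patients". Under Target Population it states that "the paediatric and adolescent patients will be defined as 1 year to less than 18 years of age".

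**The concern.** The power statement takes its sample size from one population and its comparison from another. Patients under 18 count towards the 75 per arm but cannot enter the historical placebo comparison. By the SAP's own enrolment figures at least 15 of the 166 are in that position, and section 2.3 makes no allowance for them.

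The sponsor chose to give a power figure and tied its 10% alpha to the use of 90% confidence intervals. A reader weighing an inconclusive interval against historical placebo will look back to the 66%. At 166 enrolled, the single-dose comparisons do not have it.

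**Working it through.** **Inputs**

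- Difference 34 h, common SD 98 h, alpha 0.10 two-sided, 75 per group, stated power 66% (section 2.3).
- 83 enrolled per arm, 90% confirmed (section 2.3).
- Minimum of 166 in total, at least 15 under 18 (Appendix 1).
- Randomization 1:1 (section 3.1); matching 1:1, adults only (section 4.4.2.2).
- Assumed here: exactly 15 under 18, split evenly between the arms, with the same 90% confirmation rate.

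**Step 1: patients per arm**

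- All ages: 83 × 0.90 = 74.7, rounded to 75.
- Adults: (166 − 15)/2 × 0.90 = 75.5 × 0.90 = 67.95, about 68.

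**Step 2: reproduce the stated power**

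For a rank comparison of two groups with normal data, the effective size is n × 3/π. Power ≈ Φ[(34/98) × √(n × (3/π)/2) − 1.645].

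- n = 75: effective size 71.6; 0.347 × √35.8 = 2.076; Φ(0.431) = 66.7%.
- The noncentral t version gives 66.3%, Noether's formula 65.9%, and simulated rank-sum and signed-rank tests 66–67%.

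The stated 66% is therefore correct for 75 per group. A one-sample signed-rank test with 98 h as the SD of the paired differences would give about 90%. The 66% thus corresponds to two independent groups, or to uncorrelated pairs.

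**Step 3: power for the adults analysed**

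- n = 68: effective size 64.9; 0.347 × √32.5 = 1.977; Φ(0.332) = 63.0%.
- Noncentral t gives 62.6%, Noether 62.3%, and simulation 62–63%.

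**Step 4: range** (noncentral t with the 3/π factor)

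| Per group | Power | Basis |
|---|---|---|
| 75 | 66.3% | as stated, all ages |
| 68 | 62.6% | adults at 166 enrolled |
| 60 | 58.0% | assumed further losses |
| 50 | 51.6% | assumed further losses |
| 136 | 87.4% | both doses combined, 2 × 68 |

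The SAP does not give the size of the further losses, so 60 and 50 are illustrations only. The sources of loss are baseline resistance and no dose taken (section 4.1.3), time to resolution set to missing (section 2.2.2.1), and no match found (section 4.4.2.2).

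**Step 5: enrolment needed for 75 adults per arm**

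75 × 2/0.90 + 15 = 181.7, so about 182 patients if 15 are under 18.

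**The case against.** - **The calculation itself is right.** It reproduces at 75 per group. The fault is that 75 is the wrong number for the population analysed.
- **68 is a scenario.** It needs exactly 166 enrolled, exactly 15 under 18 and an even split. Both counts are minimums, Appendix 1 allows additional patients, and the randomization stratum divides at age 12, so an even split of under-18s is not guaranteed. This stands as a caveat. However, section 2.3 itself plans on 83 per arm, and Appendix 1 ties any extension to influenza A numbers and resistance precision. At a fixed 166, more than 15 minors would lower the figure further.
- **Matching could recover the power.** With an assumed within-pair correlation of 0.10, a signed-rank test at 68 pairs has about 66–67%. But the planned Hodges-Lehmann estimate with its Moses interval is a two-sample method and does not use the pairing.
- **Nothing is decided on it.** The sample size was chosen for resistance, no hypothesis is tested, and the 90% interval half-width moves only from 1.645 × 98 × √(2/71.6) = 26.9 h to 1.645 × 98 × √(2/64.9) = 28.3 h. Moreover, section 4.4.2.2 concedes that the drug effect cannot be separated from immune status. All of this stands and keeps the point minor.
- **The comparison covered is clear enough.** Section 4.4.2.2 also plans a "Comparison of combined conventional and double dose with combined matched historical placebo", if the two doses respond alike. Section 2.3 speaks of 75 in each treatment arm, which already points to the single-dose comparisons. Naming them would help, but leaving them unnamed is not a separate fault.

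**Conclusion.** The concern holds, as a minor point. The 66% belongs to 75 patients of all ages per arm, whereas the comparison it describes uses matched adults. At 166 enrolled, with 15 under 18 split evenly and 90% confirmed, about 68 adults per arm give about 62–63% power, roughly 4 points less. At that enrolment 68 is an upper limit, because 15 is a minimum and later exclusions only reduce it. Enrolling about 182 would restore 75 adults per arm before those exclusions. The conclusion keeps the SAP's own difference, SD and alpha.

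**What to change.** Restate the power in section 2.3 along these lines:

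> For each dose arm against its matched historical placebo, about 68 adults per arm are expected if 166 patients are enrolled, 15 of them under 18, and 90% have confirmed influenza. This gives about 62% power for a difference of 34 hours (SD 98 hours, two-sided 10% alpha), before further exclusions. If 60 or 50 adults per arm are evaluable (assumption), power is about 58% or 52%. The combined-dose comparison, if made, has about 87% with 136 per group.

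Replace the signed-rank label with the two-sample rank test that corresponds to the Hodges-Lehmann and Moses interval. The label does not alter the result for uncorrelated pairs, but it should agree with the analysis. The cost is SAP wording only: conduct, data and analysis stay as they are, and the stated single-dose power falls by about 4 points.
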